7. TREATMENT COMPLIANCE

Upon termination of the study, or at the request of the sponsor or its designee, the pharmacist must return the study drug to the sponsor or its designee, after all drug supplies have been accounted for, unless it is destroyed at the site as agreed upon by both the sponsor and the site.

Instructions regarding accountability for study drug are provided in the study Site Investigational Product Manual.

7.1. Ibrutinib Compliance

The study drug (ibrutinib) is to be prescribed only by the principal investigator or a qualified physician listed as a subinvestigator on required forms. Records should be kept on the study drug accountability record provided by the sponsor or its designee. Dispensing of the study drug (ibrutinib) must be recorded in the subject's source documents. Ibrutinib may not be used for any purpose other than that outlined in this protocol, including other human studies, animal investigations, or in vitro testing.

The IWRS will be used to assign centrally supplied study treatment kits for each subject. The investigator or the site pharmacist will maintain a log of all ibrutinib dispensed and returned. Drug supplies for each subject will be inventoried and accounted for throughout the study. Subjects/caregivers will be provided with a diary card to record intake at home. Site personnel are to instruct the subject to bring the diary card and any unused ibrutinib to the site at the beginning of each treatment cycle to check ibrutinib dosing compliance.

Instructions for proper self-administration and ibrutinib storage conditions will be provided. Precautions associated with the use of ibrutinib and prohibited concomitant medications will be reviewed. Site staff will provide additional instruction to re-educate any subject who is not compliant with the ibrutinib schedule. Subjects will be asked to keep a log of ibrutinib administration and report dietary intake on PK days.

7.2. RICE/RVICI Compliance

Background therapy with RICE/RVICI will be provided by qualified study-site personnel and each administration will be recorded in the electronic CRF. The site pharmacist will maintain a log of all drug vials prepared for infusion and administration. Drug supplies, if provided by the sponsor, for each subject will be inventoried and accounted for throughout the study. The infusion will be administered according to the approved prescribing information or approved institutional guidelines.

8. PRESTUDY AND CONCOMITANT THERAPY

Systemic use of the following concomitant medications will be collected in the electronic CRF and recorded in the source documents beginning with signing of the ICF to 30 days after the last dose of the last study treatment or until the start of subsequent antilymphoma therapy (whichever is earlier): growth factors, transfusions, anti-infectives (antibacterials, antivirals, and antimycotics), steroids, anti-arrhythmics and other cardiac supportive therapy, anti-epileptics, psychoanaleptics, and any anticancer therapy (including radiation). Concomitant therapies administered at the time of, and used in the treatment of a serious adverse event, should be recorded. The sponsor must be notified in advance (or as soon as possible thereafter) of any instances in which prohibited therapies are administered.

8.1. Permitted Medications and Supportive Therapies

Concomitant medications for medical conditions other than NHL are permitted. Usage of antimicrobial prophylaxis in accordance with standard practice is permitted and should be considered in subjects who are at increased risk for opportunistic infections. Non-azole antifungal prophylaxis with coverage for aspergillosis is recommended (eg, amphotericin B or echinocandins). The use of growth factors is permitted in this study, but should be used according to institutional, provincial, or other guidelines (eg, American Society of Clinical Oncology) and according to the investigators site standard for use of growth factors during treatment of NHL with standard RICE/RVICI chemotherapy. The use of granulocyte colony stimulatory factor (GCSF) should be used with the RVICI regimen beginning on Day 12 and continued until ANC $\geq 500/\mu\text{L}$ on 2 occasions post-nadir (Table 6). Supportive therapies, other than anticancer treatment, needed for the management of subjects enrolled in this study are permitted with restrictions for corticosteroids (see Section 8.2).

8.1.1. Medications Permitted Prior to Study Treatment

Corticosteroids to control symptoms of lymphoma are permitted prior to enrollment/randomization (40 mg/m²/day prednisone or equivalent) for a maximum of 10 days. If pretreatment corticosteroids exceed 40 mg/m²/day of prednisone or equivalent, please consult the medical monitor. If steroids are administered, they should be given after the baseline imaging assessment, baseline laboratory assessments, and baseline performance status assessment. Steroids must be recorded on the electronic CRF. Treatment with steroids should be discontinued upon beginning the Treatment Phase.

8.1.2. Medications Permitted During Treatment

The following supportive therapies are recommended:

- Histamine 2 (H₂) blocker or proton pump inhibitors for peptic ulcer prophylaxis
- 5-HT₃ antagonists or equivalent antiemetics
- Uric acid-lowering agents:

Subjects with more than 1 of the factors listed below are considered to be at increased risk of tumor lysis syndrome and should be considered for hydration and treatment with a uric acid-lowering agent as well as for frequent monitoring of tumor lysis-associated signs and symptoms, including blood chemistry. Uric acid-lowering agents may include xanthine oxidase inhibitor allopurinol or Uloric[®] [febuxostat] with or without rasburicase per the drug product package inserts.

- Serum creatinine $\geq 1.5 \times \text{ULN}$ or calculated creatinine clearance $< 60 \text{ mL/min}$
- Uric acid $\geq 450 \mu\text{mol/L}$ or 7.5 mg/dL
- Bulky disease (eg, lymph node $> 10 \text{ cm}$ or massive splenomegaly)
- Elevated lactic acid dehydrogenase $> 2 \times \text{ULN}$
- Premedication with acetaminophen or equivalent, and diphenhydramine (or an antihistamine of investigator's choice).

- Loperamide for the treatment of diarrhea, starting at the time of the first watery stool. Infectious diarrhea should be ruled out prior to initiation of loperamide. The loperamide dose regimen should be according to standard practice.
- Blood product transfusions (including but not limited to platelets, red blood cells, and immunoglobulins), and growth factors, as required.
- Prophylactic treatment for pneumocystis carinii pneumonia, oral candidiasis and Herpes simplex virus infections according to local standards.
- Non-azole antifungal prophylaxis with coverage for aspergillosis (eg, amphotericin B or echinocandins) for subjects on ibrutinib. Azole antifungals are allowed for subjects randomized to background therapy only.
- A single dose of corticosteroids given as premedication prior to rituximab infusions and/or in response to infusion-related reactions.

8.2. Prohibited Medications

The following medications and supportive therapies are prohibited during the Treatment Phase:

- Any anticancer agent other than the outlined CIT regimen
- Systemic corticosteroids above that given for CIT chemotherapy and anti-emetic use (prednisone not more than 4 to 5 mg/m²/day or its equivalent is allowed for the treatment of adrenal insufficiency or other medical reason that is not cancer related). If stress dose steroids are required, the medical monitor should be informed.
- Any experimental agents other than ibrutinib

The sponsor must be notified in advance (or as soon as possible thereafter) of any instances in which prohibited therapies are administered.

8.3. Concomitant Medications to be Avoided or to be Used with Caution

[Attachment 4](#) provides instructions for medications to be avoided or used with precaution in subjects taking ibrutinib, including strong and moderate CYP3A inhibitors or inducers, and a list of these medications is provided in [Attachment 5](#). Numerous antibiotics, antivirals, antifungals, antiepileptic, and cardiac medications are included in this list. Supplements such as fish oil and vitamin E preparations should be avoided.

8.3.1. Radiation Therapy

Radiation therapy must not be given concurrently with ibrutinib. Ibrutinib should be temporarily stopped for 3 days after the last radiation treatment. Subjects should have sites of measurable disease, other than those that were irradiated, that can be followed for response. If a subject's disease progresses while on study and the subject requires radiation therapy, disease assessment evaluations should be obtained prior to initiating radiation.

8.4. Subsequent Antilymphoma Therapies

Administration of subsequent antilymphoma therapy is not allowed until:

- Confirmed residual disease after completion of at least 3 cycles of study treatment, or
- PD (or relapse after CR) any time during treatment as established according to the criteria described in Section [9.2.5.2](#), Response Categories.

Note that the medical monitor must be notified of the subject's suspected PD and all imaging, bone marrow, and cerebrospinal fluid (CSF) disease analyses are required to be centrally reviewed before a subject is removed from study therapy. Subjects who have not progressed while on therapy and who receive subsequent therapy for NHL will continue to be followed until PD. For any subsequent antilymphoma therapy, the start date, end date, and best response should be documented in the appropriate section of the electronic CRF.

9. STUDY EVALUATIONS

9.1. Study Procedures

9.1.1. Overview

The study is divided into 3 phases: a Pretreatment (Screening) Phase, a Treatment Phase, and a Posttreatment Phase. The Time and Events Schedule summarizes the frequency and timing of efficacy, pharmacokinetic, pharmacodynamic, biomarker, and safety measurements applicable to this study ([Table 1](#), [Table 2](#), [Table 3](#), and [Table 4](#)).

The estimated maximum blood volume collected from each subject for the entire study duration is approximately 139.0 to 230.5 mL in Part 1, and 131.4 to 222.9 mL in Part 2, including samples drawn for safety, pharmacokinetics, pharmacodynamics, biomarkers, protein binding (Part 1 only), and pregnancy testing (when urine is not available for testing; young women of childbearing potential only) (see [Attachment 7](#)). Blood volumes drawn should not exceed local or institutional standards.

Repeat or unscheduled samples may be taken for safety reasons or for technical issues with the samples but should not exceed allowable daily blood volume limits per local standards.

If at any time, a subject undergoes stem cell harvest in preparation for a stem cell transplant, the total cell count collected should be recorded in the eCRF.

9.1.2. Pretreatment (Screening) Phase

All subjects, or their legally-acceptable representatives, must sign an ICF prior to the conduct of any study-related procedures. Where applicable, subjects below the age of legal consent should sign an assent form prior to the conduct of any study-related procedures. During this phase, eligibility criteria will be reviewed and a complete clinical evaluation performed as specified in the Time and Events Schedule ([Table 1](#) and [Table 2](#)). The pathology report for the original diagnosis of NHL or at the time of relapse, if available, will be used to confirm diagnosis. If that pathology report is not available, the results of a fresh biopsy will be required for enrollment into

the study. The results of laboratory tests noted in the inclusion criteria must be within the limits specified prior to enrollment/randomization; testing may be repeated for this purpose. The last result obtained prior to start of study treatment will be used to determine eligibility. Assessments performed as part of the subject's routine clinical evaluation and not specifically for this study need not be repeated after signed informed consent has been obtained provided that assessments fulfill the study requirements and are performed within the specified timeframe prior to randomization ([Table 1](#) and [Table 2](#)). Echocardiography or multiple-gated acquisition scan (MUGA) is mandatory at Screening, and for subjects treated with RVICI background therapy, it is also mandatory after each cycle (before treatment on Day 1 of Cycle 2 and Cycle 3). Echocardiography or MUGA may be repeated if clinically indicated during the study (using same modality) either at an assessment visit or at an unscheduled visit.

Retesting for Eligibility

Limited retesting of abnormal Screening values that lead to exclusion are allowed only once using an unscheduled visit during the Screening period (to reassess eligibility). If a subject does not meet all inclusion and exclusion criteria (is a screen failure) but at some point in the future is expected to meet the subject eligibility criteria, the subject may be rescreened on 1 occasion only. Subjects who are rescreened will be assigned a new subject number, undergo the informed consent process, and then restart a new screening phase.

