4. SUBJECT POPULATION

Screening for eligible subjects will be performed within 14 days before administration of the study drug. The inclusion and exclusion criteria for enrolling subjects in this study are described in the following 2 subsections. If there is a question about the inclusion or exclusion criteria below, the investigator must consult with the medical monitor and resolve any issues before enrolling a subject in the study. Waivers are not allowed.

For a discussion of the statistical considerations of subject selection, refer to Section 11.2, Sample Size Determination. The last assessment/evaluation or laboratory result obtained prior to randomization will be used to determine eligibility.

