13. Criterion added per amendment 2:
 - 13.1 A diagnosis of post-transplant lymphoproliferative disease (PTLD)
14. Criterion added per amendment 2:
 - 14.1 Patients who are within 6 months of an allogeneic bone marrow transplant
15. Criterion added per amendment 4
 - 15.1 Subjects who have had prior exposure to ibrutinib

NOTE: Investigators should ensure that all study enrollment criteria have been met at Screening. If a subject's clinical status changes (including any available laboratory results or receipt of additional medical records) after Screening but before the first dose of study drug is given such that he or she no longer meets all eligibility criteria, then the subject should be excluded from participation in the study. Section 17.4, Source Documentation, describes the required documentation to support meeting the enrollment criteria.

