6. DOSAGE AND ADMINISTRATION

For the purposes of this study, 'study drug' refers to ibrutinib and 'study treatment' refers to ibrutinib and CIT. The dosages for background CIT are described in [Table 5](#) and [Table 6](#). A dosing guide for ibrutinib is provided in [Attachment 1](#). For subjects who require dosing through a feeding tube please refer to the Investigational Product Preparation Instruction (IPPI) for information on compatible tubes. All dosing information must be recorded in the Dosage Administration page of the case report form (CRF).

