9.1.3. Treatment Phase

The Treatment Phase will begin at enrollment (for Part 1) or randomization (for Part 2) and will continue until discontinuation of combination study treatment (ie, ibrutinib + CIT or CIT alone) due to disease progression, initiation of subsequent antilymphoma therapy, unacceptable toxicity, withdrawal, CR, or completion of study treatment after Cycle 3. The last measurements taken on Cycle 1 Day 1 before administration of study treatment or at Screening (whichever value was last) will be defined as the baseline values for safety assessment and treatment decision. Laboratory values obtained prior to Cycle 1 Day 1 should be repeated if they were collected more than 5 days prior to the start of ibrutinib treatment. These values should be consistent with the values in the inclusion and exclusion criteria ([Sections 4.1](#) and [4.2](#), respectively) in order for the subject to receive treatment.

A symptom-directed physical exam (including lymphoma B-symptoms) and laboratory testing will be conducted. Adverse events and changes to concomitant medications will be recorded. Subjects will be evaluated throughout this phase for possible toxicities. Dose modifications will be made as according to criteria described in the protocol (see [Section 6.2](#)).

All subjects will visit the study site on Day 1 of Cycle 1 during the Treatment Phase. Clinical evaluations and laboratory studies may be repeated more frequently, if clinically indicated. When all evaluations have been completed, and it has been determined that the subject may continue treatment, CIT will be administered intravenously and sufficient study drug will be dispensed for self-administration. The subject should refrain from taking the study drug on the morning of study visits designated for pharmacokinetic sampling until seen at the site. If a subject shows signs of progression on physical examination or laboratory assessment, the subject may continue

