5.4.2. Primary Analysis Methods for EFS

Subjects who continue to respond after 3 cycles of treatment, are progression free and alive will be censored at the date of last disease assessment. Subjects with no baseline or any post-baseline disease assessment will be censored at the date of randomization.

The analysis of the primary endpoint (EFS) will be based on the ITT population. For the primary efficacy analysis, EFS will be compared between treatment groups using a non-stratified log-rank test. The Kaplan-Meier method will be used to estimate the distribution functions of EFS for each treatment group. The number of events, subjects censored, the estimate of medians, and 90% confidence interval for the medians will be presented. The plot of EFS using the Kaplan-Meier method will be presented. The estimate of the hazard ratio between the 2 treatment groups and its associated 90% confidence interval will be computed based on the non-stratified Cox proportional hazards model.

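### Eligibility is fixed at randomization in one section but can be re-judged up to first dose in others, so a Part 2 subject can be excluded after open-label allocation and then censored at day 0.

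*Protocol*

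**What the plan says.** The protocol names more than one moment at which eligibility is decided.

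- Section 4: "The last assessment/evaluation or laboratory result obtained prior to randomization will be used to determine eligibility".
- Section 9.1.2 first requires that laboratory values "must be within the limits specified prior to enrollment/randomization; testing may be repeated for this purpose". The next sentence moves the reference point: "The last result obtained prior to start of study treatment will be used to determine eligibility".
- The note closing Section 4.2 covers a change in clinical status "after Screening but before the first dose of study drug is given such that he or she no longer meets all eligibility criteria" and gives the consequence: "then the subject should be excluded from participation in the study".
- Section 9.1.3 starts the Part 2 Treatment Phase at randomization. It says that earlier laboratory values "should be repeated if they were collected more than 5 days prior to the start of ibrutinib treatment", and it makes treatment conditional on values consistent with Sections 4.1 and 4.2.
- Section 6 defines the terms: "study drug' refers to ibrutinib and 'study treatment' refers to ibrutinib and CIT".

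Section 5 makes the trial open-label. The ITT set (Protocol 11.1, SAP 2.3.1) holds all randomized subjects as randomized. For the primary EFS analysis SAP 5.4.2 adds: "Subjects with no baseline or any post-baseline disease assessment will be censored at the date of randomization".

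**The concern.** Randomization protects the comparison only if nothing that happens after it decides who contributes outcome data. Here a subject can be randomized on qualifying values, have the arm disclosed, and be excluded from participation because a later value or change in status fails a criterion. Several criteria (neutrophils, platelets, bilirubin, creatinine, performance status) can worsen as an aggressive lymphoma advances, so those excluded may well have a poor outlook.

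ITT membership does not repair this alone. A subject who leaves before any post-baseline disease assessment can be censored at time zero, which removes that subject from every risk set in the log-rank test. If this happened more often in one arm, and to subjects with worse prognosis, the primary comparison would be biased. The documents also do not tell a site whether such a subject is withdrawn, untreated but followed, or treated as never enrolled.

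**Working it through.** **1. Time points side by side (Part 2)**

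| Place | Decided or re-checked up to | Consequence of failing | Arms reached |
|---|---|---|---|
| Section 4 | randomization | not eligible | both |
| 9.1.2, first sentence on laboratory limits | randomization | not eligible | both |
| 9.1.2, next sentence | start of study treatment | not eligible | both (ibrutinib and CIT) |
| 4.2 note | first dose of study drug | excluded from participation | unclear |
| 9.1.3 | start of ibrutinib (retest trigger) | no treatment | unclear |
| 9.8 | first dose of study treatment | laboratory retest | both |
| Table 2, footnote m | before ibrutinib or background therapy | results needed before dosing | both |
| Table 2, footnote o, with 9.8 | serology may be pending at randomization | if core antibody is positive, a negative hepatitis B PCR is needed to stay in the study | both |

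Rows 1 and 3 cannot both define eligibility. Section 10.2 lists three reasons for withdrawal from the study: loss to follow-up, withdrawn consent, and the sponsor ending the study. Loss of eligibility is not one, so the 4.2 note and 10.2 also conflict.

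**2. The planned figures are not in dispute.** Inputs from Section 11.2: 60 events, hazard ratio 0.5, 2:1 allocation, one-sided alpha 0.05. Schoenfeld power = Φ(√(60 × 2/3 × 1/3) × ln 2 − 1.645) = Φ(3.651 × 0.693 − 1.645) = Φ(0.886) = 0.81, which matches the stated 80% or more. Accrual: 72 / 1.44 = 50 months, as stated. A single eligibility time point changes neither.

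**3. Size under assumed exclusion patterns.** The documents give no rate of post-randomization exclusion, so the counts and selection rules are assumptions. The simulation has 48 ibrutinib and 24 control subjects, exponential EFS with a 5-month median in both arms (no true effect), accrual of 1.44 per month, a log-rank test rejecting at Z < −1.645, and excluded subjects censored at day 0. The analysis is at 54 months, except at 60 events for the worst-third rows.

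| Exclusion pattern | Number excluded | One-sided rejection |
|---|---|---|
| None | 0 | 5.9% (6,000 runs); 6.2% (20,000 runs) |
| Ibrutinib arm only, from worst-prognosis quarter | 1, 2, 3, 4 | 7.0, 8.3, 9.7, 10.7% |
| Ibrutinib arm only, from worst-prognosis third | 1, 2, 3, 5 | 6.9, 7.9, 9.4, 11.7% |
| Both arms alike, from worst quarter | 2 + 1; 4 + 2 | 6.2; 6.3% |
| Ibrutinib arm only, unrelated to prognosis | 2; 4 | 5.7; 5.8% |

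The Monte Carlo standard error near 6% is √(0.06 × 0.94 / 6,000) = 0.3 percentage points, or 0.2 with 20,000 runs. The baseline of about 6% rather than 5% is a feature of this test in this small 2:1 design, not of the eligibility wording. The comparison to make is with 6%.

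**The case against.** A reader might infer a stronger point. Section 6 defines study drug as ibrutinib, so the 4.2 note and the 9.1.3 retest would operate only in the ibrutinib arm, deteriorating subjects could leave that arm but not the control arm, and the bias would favour ibrutinib. The documents do not support that.

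- The 9.1.2 sentence, Section 9.8 and Table 2 footnote m all cover both arms, and in 9.1.3 all subjects attend Cycle 1 Day 1 for evaluation before CIT.
- The protocol uses study drug loosely for everyone. The 14-day screening window and exclusion criteria 1 and 8 run to its administration, and under the strict definition control subjects would have no screening window.
- Read strictly, the 4.2 note would never close for control subjects, who receive no ibrutinib. That is not the same as sparing them.

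A second objection is that day-0 censoring is not inevitable. Section 9.2.5 continues efficacy assessments to progression, Section 10.2 continues scheduled assessments after early stopping of treatment, and SAP Table 3 counts all progressions and deaths. This stands in part. But the 4.2 note excludes the subject from the study rather than only from treatment, Section 10.2 asks for assessments after study withdrawal only where possible, and SAP 5.4.2 states no exception for a death without an assessment. The outcome for such a subject is undetermined.

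A third objection is that enrollment stopped after the futility boundary was reached (Section 11.9.1), so new eligibility wording has nobody to act on. That is right for recruitment. It does not settle how subjects already randomized are followed and analysed.

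**Conclusion.** The conflict over when eligibility is decided is real and nothing in the documents resolves it. In Part 2 it permits exclusion after open-label allocation, contradicts the withdrawal rules, and can end in censoring at randomization.

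A bias in a known direction is not established. It would need exclusions that differ between arms and also relate to prognosis. If both held in the ibrutinib arm for 1 to 4 subjects, one-sided rejection under no effect would rise from about 6% to about 7 to 11%. If exclusions were symmetric or unrelated to prognosis, there would be no material inflation. These figures assume the counts, the selection and day-0 censoring with no later events recovered. How many such subjects exist, and in which arm, is not stated.

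The point does not undermine the futility outcome: in the modelled one-arm scenario the distortion would have favoured ibrutinib.

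**What to change.** **Protocol, Part 2.** Reconcile Section 4, the 4.2 note, 9.1.2, 9.1.3, 10.2 and the pending-serology rule (Table 2 footnote o, Section 9.8). Eligibility should be determined once, on the last values available before randomization. Any later pre-dose check should be worded identically for both arms and govern treatment only; its clinical content is for the sponsor to settle. State that every randomized subject, treated or not, stays in follow-up for EFS and survival unless consent is withdrawn or contact is lost.

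**SAP 5.4.2.** Amend it so that a death or documented progression in a subject without a post-baseline assessment counts as an EFS event, in line with SAP Table 3, instead of being censored at randomization. Report randomized-but-untreated subjects by arm, with the reason and last known status.

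**Cost.** Wording changes and follow-up of what is likely to be a handful of subjects under existing schedules. The 72 subjects, 60 events and power of 0.81 in the design are unaffected. Because enrollment has ceased, the benefit lies in tracing and correctly analysing subjects already randomized. The by-arm table would show whether the issue ever arose.
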